6.4.3.5 AC-assessed Mycological Response

| | Category | Outcome |
|---------------|-------------------------|--|
| Success | Eradication | No growth of the original (at baseline) causative organism on culture or identified by histology/cytology on post baseline (after day 7) cultures and/or histology/cytology |
| | Presumed eradication | Missing post baseline documentation of eradication of the original causative organism at baseline PLUS resolution of all or some clinical symptoms/physical finding |
| Failure | Persistence | Persistence of the original causative organism cultured or identified by histological /cytology at baseline or ?? |
| | Presumed Persistence | Missing post baseline documentation of the persistence of the original causative organism at baseline PLUS no resolution or worsening of any clinical symptoms/physical findings |
| Not Evaluable | No Mycological Evidence | |

6.4.3.6 AC-assessed Radiological Response

| Summary | Category | Outcome |
|----------------|----------------------------|---|
| Success | Complete: | ≥ 90% improvement |
| | Partial | At least < 25% response at day 42 and at least 50% by Day 84 |
| Failure | Stable | Minor or no change in radiographic abnormalities associated with IFD, but no signs of progression |
| | Progression | Worsening or new radiological abnormalities associated with IRD |
| Not Evaluable | No Post baseline Radiology | No post baseline Radiology available with baseline evidence of radiolical disease |
| | Radiology | Radiology not applicable at baseline |

6.4.3.7 AC-assessed Attributable Mortality

| Category | Outcome |
|------------------------------------|--|
| Directly Due to IFD | Death directly due to consequences of progressive IFD (clear evidence that mortality is due to progressive IFD) |
| Evidense Death Associated with IFD | Death associated with evidence of residual or ongoing IFD at time of death, but death may be due to IFD or progression of underlying disease |
| No Evidense Death Associated | Death associated with no evidence of residual or ongoing IFD) |
| Indeterminant | Indeterminant Cause |
| No Known Death | No Known Death |

6.4.3.8 AC-assessed Overal Response

| Category | Outcome |
|-----------------|---|
| Success | 
 • Complete-Success • Partial-Success |
| Failure | 
 • Stable-Failure • Progression-Failure |
| Not Evaluable | 
 • Results Not Evaluable |

6.4.4 Other Secondary Endpoints

Population pharmacokinetics and/or pharmacokinetic/pharmacodynamics analyses will be performed by modeling and simulation scientist. All details of the population pharmacokinetic analysis will be

described in a separate analysis plan and a separate population pharmacokinetic modeling report will be written.

6.5 Analysis of Safety

All safety data will be presented for the SAF population. AEs will be coded using MedDRA. Frequency and percentage will be presented for each category.

6.5.1 Adverse Events

TEAE is defined as an AE observed after starting administration of the study drug through 30 days after EOT. The number and percentage of subjects with treatment-emergent AEs, serious adverse events (SAEs), AEs leading to withdrawal of treatment, and AEs related to study drug will be summarized by MedDRA system organ class, MedDRA High Level term, and MedDRA preferred term for overall subjects and by subjects in each age cohort. The number and percentage of AEs by severity will also be summarized. All AEs will be listed.

A study drug-related TEAE is defined as any TEAE with a causal relationship of YES by the investigator. The incidence of treatment emergent AEs will be summarized by relationship to study drug and severity for all subjects and by each age cohort. The protocol defines how Treatment Emergent AEs are determined. Although all AEs are collected, the summary Table will be based on the TEAEs.

Clinically significant out-of-range laboratory findings are to be determined and documented by the investigator/subinvestigator who is a qualified physician. Clinically significant changes will be recorded as AEs.

An overview table will include the following:

- Number of TEAEs,
- Number and percentage of subjects with TEAEs,
- Number of drug related TEAEs,
- Number and percentage of subjects with drug related TEAEs,
- Number of serious TEAEs,
- Number and percentage of subjects with serious TEAEs,
- Number of serious drug related TEAEs,
- Number and percentage of subjects with serious drug related TEAEs,
- Number of TEAEs leading to permanent discontinuation of study drug,
- Number and percentage of subjects with TEAEs leading to permanent discontinuation of study drug, and
- Number of deaths.

The number and percentage of subjects with TEAEs, as classified by SOC, High Level Term (HLT), and PT will be summarized. Summaries will be provided for the following:

- TEAEs

- drug related TEAEs,
- serious TEAEs,
- drug related serious TEAEs,
- TEAEs leading to permanent discontinuation of study drug,
- drug related TEAEs leading to permanent discontinuation of study drug,

The number and percentage of subjects with TEAEs, as classified by SOC and PT will be summarized by time interval. For each adverse event in a particular interval, a subject will be counted if there is an onset of a treatment-emergent adverse event regardless of onset in other intervals.

The number and percentage of subjects with TEAEs, as classified by SOC and PT will be summarized by subgroups defined in Section 6.5.7.

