A formal statistical justification of the sample size is not made. The sample size of approximately 30 subjects is planned. Every effort will be made to achieve at least 5 evaluable subjects per age cohort: 1 to < 12 years of age and 12 to < 18 years of age. The sponsor reserves the right to stop enrollment if the cohort requirements are not achieved.

Safety

All AEs will be listed by subject and by age cohort. The incidence of the following AEs will be summarized by system organ class and preferred term for overall subjects and by subjects in each age cohort: overall, serious, related to study drug and leading to the permanent discontinuation of study drug.

Vital signs will be listed and summarized. Laboratory test values will be presented in shift tables and by individual listings with flagging of values outside the normal reference ranges. ECG findings will be presented by listings and frequency tables, as appropriate.

The incidence of treatment emergent AEs will also be summarized by relationship to study drug and severity for all subjects and by subjects in each age cohort.

Efficacy

Per each diagnosis (IA or IM) accrued, the crude all-cause mortality rates will be calculated by dividing the number of deaths by the number of subjects in the full analysis set (FAS) (i.e., all enrolled subjects who received at least one dose of study drug), and a 2-sided exact 95% CI will be calculated. Each subject will be classified as either death or alive. Subjects who died on or before day 42/day 84/EOT, as well as subjects who are lost to follow-up before day 42/day 84/EOT will be counted as deaths.

Efficacy (*continued*)

Crude success rates and 2-sided exact 95% CIs will be calculated for the overall, clinical, radiological and mycological response at day 42, day 84 and EOT in the FAS.

For each efficacy endpoint, a summary will be presented for overall subjects and by subjects in each age cohort.

Pharmacokinetics

Observed plasma concentration data for isavuconazole will be presented in listings.

In addition, pharmacokinetic plasma concentrations will be analyzed using population pharmacokinetic model. Details of the model and modeling procedure will be provided in separate modeling report.

Pharmacodynamics

Not applicable.

Interim Analyses

Not applicable.

[figure not shown]
Data and Safety Monitoring Board and Adjudication Committees

A Data and Safety Monitoring Board will be utilized to monitor subject safety throughout the study.

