5.5 Adverse Events and Other Safety Aspects

5.5.1 Definition of Adverse Events

An AE is any untoward medical occurrence in a subject administered a study drug, and which does not necessarily have to have a causal relationship with this treatment. An AE can therefore be any unfavorable and unintended sign (including an abnormal laboratory finding), symptom or disease (new or exacerbated) temporally associated with the use of a medicinal product whether or not considered related to the medicinal product.

In order to identify any events that may be associated with study procedures and could lead to a change in the conduct of the study, Astellas collects AEs even if the subject has not received study drug treatment. AE collection begins after the signing of the ICF and will be collected until 60 days after the last dose of study drug or the subject is determined to be a screen failure.

Care will be taken not to introduce bias when detecting AEs and/or SAEs. Open-ended and non-leading verbal questioning of the subject is the preferred method to inquire about AE occurrences.

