5.5.5 Reporting of Serious Adverse Events (SAEs)

The collection of AEs and the expedited reporting of SAEs will start following receipt of the ICF and will continue until 60 days after last administration of study drug or the subject is determined to be a screen failure.

In the case of a SAE, the investigator must contact the sponsor by fax or email immediately (within 24 hours of awareness).

The investigator must complete and submit an SAE worksheet containing all information that is required by local and/or regional regulations to the sponsor by email or fax immediately (within 24 hours of awareness).

The SAE worksheet must be signed by a medically qualified investigator (as identified on Delegation of Authority Log). Signature confirms accuracy and completeness of the SAE data, as well as the investigator causality assessment including the explanation for the causality assessment.

For contact details, see [Section II Contact Details of Key Sponsor's Personnel]. Fax or email the SAE/Special Situations worksheet to:

Astellas Pharma Global Development – US
Pharmacovigilance
[contact] or [contact]
Email: [contact]

If there are any questions, or if clarification is needed regarding the SAE, please contact the sponsor's medical monitor/study physician or his/her designee [Section II Contact Details of Key Sponsor's Personnel].

Follow-up information for the event should be sent promptly (within 7 days of the initial notification).

Full details of the SAE should be recorded on the medical records, SAE/Special Situation Worksheet and on the eCRF.

The following minimum information is required:

- International study number/study number,
- subject number, sex and age,
- the date of report,
- a description of the SAE (event, seriousness criteria),
- causal relationship to the study drug (including reason), and
- the drug provided (if any).

The sponsor or sponsor's designee will medically evaluate the SAE and determine if the report meets the requirements for expedited reporting based on seriousness, causality and expectedness of the events (e.g., Suspected Unexpected Serious Adverse Reaction [SUSAR] reporting) according to current local/regional regulatory requirements in participating countries. The sponsor or sponsor's designee will submit expedited safety reports (e.g., IND

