7.5 Analysis of Safety

7.5.1 Adverse Events

AEs will be coded using MedDRA.

TEAE is defined as an AE observed after starting administration of the study drug through 30 days after the last dose. The number and percentage of subjects with treatment-emergent AEs, SAEs, AEs leading to withdrawal of treatment and AEs related to study drug will be summarized by MedDRA system organ class, MedDRA preferred term for overall subjects and by subjects in each cohort. The number and percentage of AEs by severity will also be summarized. All AEs will be listed.

A study drug-related TEAE is defined as any TEAE with a causal relationship of YES by the investigator.

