6.9 Analysis Windows

AEs and Vital signs will be summarized using Analysis Windows as below:

| Analysis Visits | Analysis Windows |
|------------------------|---|
| Baseline | Day(s) <=1 up to initiation of first dose |
| Day 2 | Day 2 |
| Day 3 | Day 3 |
| Day 7 | Day 5 to 9 |
| Day 14 | Day 12 to 16 |
| Day 21 | Days 19 to 23 |
| Day 28 | Days 26 to 30 |
| Day 35 | Days 33 to 37 |
| Day 42 | Days 40 to 44 |
| Day 49 | Days 47 to 51 |
| Day 56 | Days 54 to 58 |
| Day 63 | Day 61 to 65 |
| Day 70 | Days 68 to 72 |
| Day 77 | Days 75 to 79 |

Cont.

| | |
|----------------------|-----------------|
| Day 84 | Days 80 to 91 |
| Day 110 | Days 103 to 117 |
| Day 140 | Days 133 to 147 |
| Day 85 ¹ | Days 81 to 100 |
| Day 115 ¹ | Days 101 to 130 |
| Day 145 ¹ | Days 143 to 147 |
| Day 210 ¹ | Days 203 to 217 |
| Day 240 ¹ | Days 233 to 247 |

¹Applies to IM and IA/IM subjects.

See Appendix 1 for details of parameters for visit windows.

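### Adverse events are collected for 60 days after the last dose, but the SAP's tables stop at 30 days, so late non-fatal serious and drug-related events would only be listed and some follow-up windows would show zeros created by the definition

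*SAP*

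**What the plan says.** **Collection.** Protocol 5.5.1 says that AEs "will be collected until 60 days after the last dose of study drug". Protocol 5.5.5 says that AE collection and expedited reporting of serious AEs (SAEs) "will continue until 60 days after last administration of study drug".

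**Definition.** Protocol 7.5.1: "TEAE is defined as an AE observed after starting administration of the study drug through 30 days after the last dose". SAP 6.5.1: "TEAE is defined as an AE observed after starting administration of the study drug through 30 days after EOT". The protocol's key terms define end of treatment (EOT) as the date of the last dose, so the two definitions agree.

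**Tables planned in the synopsis.** The safety paragraph under Statistical Methods plans incidence by system organ class and preferred term (SOC/PT) for these AE categories: "overall, serious, related to study drug and leading to the permanent discontinuation of study drug". It does not limit them to TEAEs. A later sentence adds TEAE summaries by relationship and severity.

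**Tables planned in the SAP.** Section 6.5.1 says: "Although all AEs are collected, the summary Table will be based on the TEAEs". Every item in its overview table names TEAEs, except the count of deaths. So do all six summaries by SOC, High Level Term and PT, and the table by time interval. The same section says: "All AEs will be listed".

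**Windows.** SAP 6.9: "AEs and Vital signs will be summarized using Analysis Windows as below". The rows include Day 110, Day 140, Day 210 and Day 240. The last two are footnoted to mucormycosis (IM) and mixed aspergillosis/mucormycosis (IA/IM) subjects. Day 140 has no footnote in 6.9, but SAP Appendix 1 labels it as follow-up for aspergillosis (IA).

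**The concern.** Safety is the first-listed objective, and the 60-day follow-up exists to serve it. If only TEAEs are tabulated, a serious or drug-related event with onset 45 days after the last dose is recorded and reported to the sponsor but enters no incidence table. With about 30 children, a single such event is material, and its absence from the tables would not be apparent.

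The windows add a second problem. A follow-up row that no TEAE can reach shows zero events whatever happened to the subjects, and a reader could take that zero as evidence of safety. The SAP also pulls against itself. Section 6.1 says that IM and IA/IM subjects are reported through the 60-day follow-up, and 6.9 provides AE windows for it, but 6.5.1 counts only treatment-emergent onsets in each interval.

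**Working it through.** **Inputs.** AE and SAE collection runs to last dose + 60 days (Protocol 5.5.1, 5.5.5). TEAEs run to EOT + 30 days (Protocol 7.5.1, SAP 6.5.1). The latest EOT is day 84 for IA and day 180 for IM (Protocol, key terms). The EOT visit has a window of ±7 days (Protocol Tables 1 and 2), so day 91 and day 187 serve as late variants.

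**The plan's own windows.** 140 ± 7 = 133 to 147, and 240 ± 7 = 233 to 247. Both match SAP 6.9.

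**Share of follow-up outside the TEAE tables.**
- Of the post-treatment period: (60 − 30)/60 = 50%.
- Of the whole period from day 1 at maximum treatment: IA 30/(84 + 60) = 30/144 = 20.8%; IM 30/(180 + 60) = 30/240 = 12.5%.

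**Can a TEAE reach the windows?** The last possible TEAE day is EOT + 30.

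| Group | EOT | Last TEAE day | Window | Overlap |
|---|---|---|---|---|
| IA | 84 | 114 | Day 140 (133-147) | 0 days |
| IA, late | 91 | 121 | Day 140 (133-147) | 0 days |
| IM | 180 | 210 | Day 240 (233-247) | 0 days |
| IM, late | 187 | 217 | Day 240 (233-247) | 0 days |

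To reach Day 240, EOT would have to be day 233 − 30 = 203 or later, which is beyond the maximum. To reach Day 140, EOT must be day 133 − 30 = 103 or later. That is impossible for IA but possible for IM, and an IM subject with EOT on day 147 − 30 = 117 or later can have TEAEs on all 15 days.

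**The 30-day rows.** With EOT on day 84, TEAEs can fall on days 103-114 of the Day 110 window, 12 of its 15 days. With EOT on day 180 they can fall on days 203-210 of the Day 210 window, 8 of its 15 days.

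**If AEs to 60 days filled the same windows.** An IA subject with EOT on day 84 is covered to day 144, so 12 of the 15 days of the Day 140 window can hold events. An IM subject with EOT on day 180 is covered to day 240, so 8 of the 15 days of the Day 240 window can.

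**Subjects who stop early.** Treatment may stop on a successful outcome. An IA subject with EOT by day 72 has collection end by 72 + 60 = day 132, before the Day 140 window opens. An IM subject with EOT by day 172 has it end by 172 + 60 = day 232, before the Day 240 window opens. Longer coverage alone therefore does not repair fixed study-day windows.

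**The case against.** The strongest reply is that the SAP follows the protocol's own statistical section. Protocol 7.5.1 has the same 30-day definition and almost the same summary sentence, and the synopsis states no 60-day period for its tables. All AEs are listed, SAEs are reported promptly through day 60, and a monitoring board reviews safety. In a descriptive study of about 30 subjects, a listing of late events can be read line by line. Much of this stands. A 30-day TEAE definition is not an error, and the SAP did not invent it. What remains is that the synopsis plans AE tables with TEAE tables in addition, while the SAP bases its summary on TEAEs alone. A listing gives no incidence by SOC/PT.

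A reader might infer more than the documents support:

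- *That every AE summary stops at 30 days.* The count of deaths in the overview table carries no TEAE limit. The opening sentence of 6.5.1 names SAEs and related AEs without making clear whether the treatment-emergent limit covers them, and its severity sentence says only AEs.
- *That late deaths appear only in listings.* Besides that count, SAP 6.1 has Kaplan-Meier mortality use all survival data to day 240 if IM subjects are included, and 6.4.2.1 presents cumulative mortality by the end of the study.
- *That the Day 140 row is empty for everyone.* Section 6.9 does not restrict it, and IM subjects still on treatment can contribute.
- *That a zero column will certainly be printed.* Table formats are in separate specifications, and 6.5.1 does not say that its time intervals are the 6.9 windows.

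**Conclusion.** The point holds for non-fatal SAEs and drug-related AEs with onset on days 31-60 after the last dose. As SAP 6.5.1 is most naturally read, they reach the listings but no incidence table. That is half of the post-treatment follow-up, or 20.8% (IA) and 12.5% (IM) of the whole observation period at maximum treatment. The Day 240 AE window is empty by construction, and the Day 140 window is empty for IA subjects, even when EOT is a week late.

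This rests on two readings: that the sentence basing the summary on TEAEs governs the ambiguous SAE wording before it, and that AEs are tabulated in the windows of 6.9, as that section says. If the SAE wording was meant to reach 60 days, the SAP needs to say so.

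The case does not depend on an expected number of late events. The documents give no rate for late non-fatal SAEs or drug-related AEs. A count derived from the cited 12-week mortality would measure deaths, which are partly summarised elsewhere. The primary endpoint is unaffected; what changes is what the safety tables report.

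**What to change.** 1. Keep the TEAE tables as planned.
2. Add SOC/PT tables of SAEs, fatal AEs and drug-related AEs from first dose to 60 days after the last dose.
3. State in SAP 6.5.1 that the SAE and death counts cover that period, which removes the ambiguity in its opening sentence.
4. For AEs, replace the Day 110, 140, 210 and 240 rows of SAP 6.9 with windows relative to the last dose (days 1-30 and days 31-60), filled from all collected AEs, or delete those rows for AEs. Relative windows let subjects who stop early contribute.

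The cost is two or three extra tables and a short SAP edit. No new data are needed.

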6.5.2 Clinical Laboratory Evaluation

Clinical laboratory samples will be collected and reported based on timepoints as listed in the Protocol Table 1 and Table 2 in Section 1 based on lab sample collection visits.

Clinical Laboratory variables will be created for each of the following:

| Chemistry: | Hematology: |
|--|--|
| Sodium | Red blood cells |
| Potassium | White blood cells (total leukocytes) |
| Magnesium | Hemoglobin |
| Calcium | Hematocrit |
| Chloride | Platelets (thrombocytes) |
| Glucose | Neutrophils (ANC) |
| Creatinine | Eosinophils |
| Creatine phosphokinase/Creatine kinase | Basophils |
| Alkaline phosphatase (ALP) | Lymphocytes |
| | Monocytes |
| | Blast cells |
| Hepatic Panel: | Pregnancy Test: |
| Albumin | Human chorionic gonadotropin (hCG) |
| Total bilirubin (TBL) | |
| Direct Bilirubin | |
| Total Protein | |
| Alanine aminotransferase (ALT) | |
| Aspartate aminotransferase (AST) | |
| | Other: |
| | Serum galactomannan (GM) |
| | Partial thromboplastin time/international normalized ratio (PTT/INR) |

The baseline value will be the last non-missing value taken on or prior to first dose of study drug. Quantitative values evaluated by the central laboratory including hematology and biochemistry will be summarized using mean, standard deviation, minimum, maximum and median at each analysis visit. Additionally, a within-subject change will be calculated as the post-baseline measurement minus the baseline measurement and summarized in the same

way. Clinical Laboratory data will be reported using the SAF population by Clinical Laboratory Tests collected at baseline and days 7, 28, 56 and 84 (or EOT).

Shifts relative to normal ranges from baseline to each time point during treatment period in lab tests will also be tabulated. Laboratory data will be displayed in listings. For quantitative laboratory measurements descriptive statistics will be used to summarize results and change from baseline for subjects.

Each laboratory result will be classified as low, normal, or high at each visit according to the laboratory supplied reference ranges as specified in the Protocol.

6.5.3 Liver Safety Assessment

The liver safety assessments will be summarized by the categories below based on the measurement from Alkaline Phosphatase (ALP), Alanine Transaminase (ALT), total bilirubin (TBIL), Aspartate Transaminase (AST), and their combination. These parameters will be based on measurements from a central laboratory.

The subjects highest value from Day 1 to Day 84 IA or Day 180 IM or EOT will be used. This criterion is without regards to the subjects baseline value.

- ALT > 3xULN, > 5xULN, > 10xULN, > 20xULN
- Total Bilirubin > 2xULN
- (ALT or AST > 3xULN) and Total Bilirubin > 2xULN
- (ALT or AST > 3xULN) and ALP < 2xULN and Total Bilirubin > 2xULN

The last 2 criteria to where 2 or more parameters are evaluated will be with the measurements on the same day or up to 1 day apart. The samples within 1 day to be considered. For example, if ALT is on day 10, ALP is on day 11 and TBIL is on day 12, this data should be considered. If ALT and ALP is on day 10, and TBIL is on day 11, this data should be considered.

The samples within 1 day apart can be used however the last criterion with 2 parameters, all 3 should be from the same day to be considered. For example, if ALT is on day 10

An eDish display plot of all patients will be created. The step-one eDISH including ALT alanine aminotransferase, TBL total bilirubin, eDISH evaluation of drug-induced serious hepatotoxicity, ULRR upper limit of reference range or normal will be created with all patients plotted.

